9.7. Daily CGM Data Summary

For daily CGM summary variables, first determine the values within each day, then average across days within a visit. The hourly mean glucose will be calculated as the mean across all CGM values collected, based on actual local time for the subject.

9.8. AUC

Area under the curve (AUC) during a period (24-hour, daytime, or nighttime) will be calculated using the standard linear trapezoidal method as defined previously in Section 9.3, by multiplying the sum of trapezoids by (the length of the period)/(the length of the period - total length of gaps that are not counted into the calculation of the AUC).

9.9. Highest Postprandial Glucose

9.9.1. *Time to the highest postprandial glucose within 4 hours after Meals*

Time from start of meal to the highest postprandial glucose level will be calculated as the time from start of meal to the maximum glucose value within 4 hours after meals, excluding the data from patients who have had the next meal event. If there are multiple time points with the maximum glucose value, then the earliest time will be used.

9.9.2. *Highest Postprandial Glucose Level within 4 hours after Meals*

Highest postprandial glucose level excursions within 4 hours after meals, will be calculated as the maximum glucose value during 0 to 4 hours after start of meal, excluding the data from patients who have had the next meal event.

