6.13. CGM Analyses

The analyses described in Section 6.13 will include data collected from first dose to last dose of study drug (ie, open-label Humalog used during the lead-in period or IP used during each of the randomized treatment periods [Period I and Period II]), excluding data (if any) that are collected while patients temporarily are off pump or off study treatment.

All of the variables will be derived for the lead-in period, Period I, and Period II. For the lead-in period, the variables will be derived based upon the data collected during the 2-week open-label Humalog treatment period. For Period I and Period II, the variables will be derived for 0 to 2, 2 to 4, and 0 to 4 weeks relative to the start of each randomized treatment period, respectively. Due to the crossover design, treatment comparisons will be based upon the derived outcome variables for 2 to 4 weeks.

Table ITSM.6.6 lists all numerical measures for CGM data, including all primary, secondary and exploratory CGM outcome variables.

To ensure that the CGM outcome variables are only calculated from CGM session days with sufficient data within the 24-hour, daytime (0600 hours to midnight), or nighttime (midnight to 0600 hours) periods, the following criteria will be used to determine a valid CGM session day to be counted into the calculation for a visit: minimum number of measures per day – at least 70% of the total measures that are supposed to be obtained, i.e. 70% of the 288 measures for the 24-hour period;

Similarly, for the by-meal outcome variables, the following criteria will be used to determine a valid CGM session day for a visit: minimum number of measures per day – at least 70% of the total measures that are supposed to be obtained. For example, 70% of the 24 measures for the iAUC_{0-2hr} after breakfast.

The definition and derivation of these variables are described in detail in [Appendix 1](#).

Table ITSM.6.6. Outcome Measures of CGM Data

Category	Endpoints	24-Hour	Daytime ^a	Nighttime ^b	By Meal ^c
Efficacy Endpoint: Glucose in the Target Ranges					
	Duration (in minutes) and percentage of time with sensor glucose values within target range 70 to 180 mg/dL [3.9 and 10.0 mmol/L], both inclusive (Primary Efficacy Endpoint)	X	X	X	X
	Duration (in minutes) and percentage of time with sensor glucose values within target range 70 to 140 mg/dL [3.9 and 7.8 mmol/L], both inclusive	X	X	X	X

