	Duration (in minutes) and percentage of time with sensor glucose values ≤180 mg/dL [10.0 mmol/L]	X	X	X	X
Efficacy Endpoint: Incremental AUCs (iAUCs) (after the start of meals)					
	iAUC _{0-1hr}				X
	iAUC _{0-2hr}				X
	iAUC _{0-3hr}				X
	iAUC _{0-4hr}				X
Efficacy Endpoint: Mean Glucose Excursions (after the start of meals) ^d					
	mean sensor glucose excursions 0 to 1 hour				X
	mean sensor glucose excursions 0 to 2 hour				X
	mean sensor glucose excursions 0 to 3 hour				X
	mean sensor glucose excursions 0 to 4 hour				X
Efficacy Endpoint: Hyperglycemic Episodes					
	Duration (in minutes) and percentage of time with glucose values >180, 181-250 and >250 mg/dL [10.0, 13.9, and 16.7 mmol/L] and hyperglycemic episodes, defined as at least 10 consecutive minutes >180, 181-250 and >250 mg/dL [10.0, 10.1-13.9 and 13.9 mmol/L]	X	X	X	
	Rate (events/patient/year) and incidence (percent of patients with at least 1 event) of hyperglycemic episodes, defined as at least 10 consecutive minutes >180 and >250 mg/dL [10.0 and 13.9 mmol/L]	X	X	X	

Outcome Measures of CGM Data

Category	Endpoints	24-Hour	Daytime ^a	Nighttime ^b	By Meal ^c
Efficacy Endpoint: Daily CGM Data Summary					
	Area under the curve (AUC)	X	X	X	
	Mean sensor glucose	X	X	X	
	Median sensor glucose	X	X	X	
	Hourly mean sensor glucose	X			
	Hourly median sensor glucose				
Efficacy Endpoint: Glucose Variability and Risk Assessment					
Within-Day	CV	X	X	X	X
	SD	X	X	X	X
	IQR	X	X	X	X
	MAGE	X	X	X	X
	LBG1: frequency and extent of low BG readings	X	X	X	X
	HBGI: frequency and extent of high BG readings	X	X	X	X
	BGRI = LBG1 + HBGI: a measure of overall variability and risks of hypo- and hyperglycemia	X	X	X	
Between-Day	CV	X	X	X	
	SD	X	X	X	
	MODD	X	X	X	
Overall ^e	CV	X	X	X	
	SD	X	X	X	
	IQR	X	X	X	
	LBGI	X	X	X	
	HBGI	X	X	X	
	BGRI	X	X	X	
Efficacy Endpoint: Highest Postprandial Glucose					
	Time from start of meal to the highest postprandial glucose level (minutes) within 4 hours after meal(s)				X
	Highest postprandial glucose level within 4 hours after meal(s)				X
	Highest postprandial glucose excursion level within 4 hours after meal(s)				X

Outcome Measures of CGM Data

Category	Endpoints	24-Hour	Daytime ^a	Nighttime ^b	By Meal ^c
Safety Endpoint: Hypoglycemic Episodes ^f					
	Duration (in minutes) and percentage of time with sensor glucose values <54, 54-69 and <70 mg/dL of hypoglycemic episodes, defined as at least 10 consecutive minutes <54 and <70 mg/dL [3.0, 3.0-3.8 and 3.9 mmol/L]	X	X	X	X

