	Rate (events/patient/year) and incidence (percent of patients with at least 1 event) of hypoglycemic episodes, defined as at least 10 consecutive minutes <54 and <70 mg/dL [3.0 and 3.9 mmol/L]	X	X	X	X
Safety Endpoint: Other					
	Duration (in minutes) of hypoglycemic episode (defined as at least 10 consecutive minutes <54 and <70 mg/dL [3.0 and 3.9 mmol/L])	across all hypoglycemic episodes with duration at least 10 consecutive minutes			
	Duration (in minutes) of each individual hypoglycemic episode (defined as at least 10 consecutive minutes <54 and <70 mg/dL [3.0 and 3.9 mmol/L])	across all hypoglycemic episodes with duration at least 10 consecutive minutes			

Abbreviations: AUC = area under curve; BGRI = blood glucose risk index; CGM = continuous glucose monitoring; CV = coefficient of variation; HBGI = high blood glucose index; hr = hour; IQR = interquartile range; LBGI = low blood glucose index; MAGE = mean amplitude of glycemic excursions; MODD = mean of daily differences; SD = Standard deviation.

^a Daytime: 0600 hours to midnight (06:00:00-23:59:59 on the 24-hour clock).

^b Nighttime: midnight to 0600 hours (00:00:00-05:59:59 on the 24-hour clock).

^c By meals: for morning (breakfast), midday (lunch) and evening (dinner) meals and overall (average across all meals). **CCI**

When calculating time in ranges (target, hypo, hyper) for meals (0 to 1 hour, 0 to 2 hours, 0 to 3 hours and 0 to 4 hours), any data that are collected after the next meal event will be excluded.

^d Mean sensor glucose measured at different time points (1, 2, 3 or 4 hours) after the start of the meal minus mean sensor glucose at the start of meal

^e Overall variability refers to the variability calculated based upon all the CGM measurements collected across all valid days for each derivation period (e.g. 2 to 4 weeks relative to the start of each of the randomized treatment period).

^f In addition, postprandial hypoglycemia episodes during the following time interval after each meal and overall will also be derived: 0 to 1 hour, 0 to 2 hours, 2 to 4 hours, 0 to 4 hours. The calculation will exclude the data from patients who have had the next meal event (according the CareLink raw data) before the end of time interval.

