9.4. Mean Sensor Glucose Excursions

Mean sensor glucose excursions in a postmeal time interval (0-1 hr, 0-2 hr, 0-3 hr or 0-4 hr) will be calculated by averaging all excursion values within the time interval. Excursions will be derived by subtracting glucose values by the starting glucose concentration, which is the average of the CGM values in the time window [-19, 0] mins relative to the start of the meal (at most 3 interstitial glucose measures).

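### SAP 9.9.2 mixes level and excursion, so the separately listed highest postprandial excursion either duplicates the peak level or has no derivation of its own

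*SAP*

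**What the plan says.** SAP Section 6.13, Table ITSM.6.6, has two separate by-meal rows under the highest-postprandial-glucose category, apart from the time-to-peak row: "Highest postprandial glucose level within 4 hours after meal(s" and "Highest postprandial glucose excursion level within 4 hours after meal(s". The text before the table states: "The definition and derivation of these variables are described in detail in" Appendix 1.

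Appendix 1, Section 9.9, has two subsections. 9.9.1 covers the time to the peak. 9.9.2 is headed "Highest Postprandial Glucose Level within 4 hours after Meals", but its one sentence begins "Highest postprandial glucose level excursions within 4 hours after meals, will be calculated as the maximum glucose value during 0 to 4 hours", followed only by the start of the meal as reference and the exclusion for a next meal. No starting value is subtracted.

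Section 9.4, on mean excursions, does say what an excursion is: "Excursions will be derived by subtracting glucose values by the starting glucose concentration".

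The outcome is exploratory under Section 6.9.3. Section 6.13 still sends it to a treatment comparison, because continuous CGM variables without another stated method go to the MMRM, as actual values and, where applicable, as change from baseline.

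**The concern.** Two outcomes are listed, and one formula is given under wording that points to both. A programmer who follows 9.9.2 to the letter produces an excursion row identical to the level row. One who treats *excursions* as a slip finds no instruction for the excursion row and has to infer one.

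The two routes give different numbers under the same label. A peak level depends on where glucose stood before the meal as well as on how far it rose. The study rationale (Protocol Section 3.1) turns on limiting rapid glucose changes after meals, and a peak level does not isolate those changes. If a peak were reported as an excursion, a premeal difference between the insulins would appear as a difference in the postprandial rise.

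**Working it through.** The plan states no figure for this outcome, so there is none to reproduce. The check is a comparison of texts followed by short algebra.

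**Texts side by side**

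1. Table ITSM.6.6: level and excursion are distinct rows, both by meal.
2. 9.9.2 heading: level. 9.9.2 sentence: *level excursions*. 9.9.2 formula: maximum glucose, nothing subtracted.
3. 9.4: excursion is glucose minus a starting concentration, which is the "average of the CGM values in the time window [-19, 0] mins relative to the start of the meal".
4. Footnote d of Table ITSM.6.6, attached to the mean-excursion rows only: mean sensor glucose at the set times "after the start of the meal minus mean sensor glucose at the start of meal".
5. 9.3: every iAUC trapezoid subtracts G0, taken from the same window as in 9.4.

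Items 3 to 5 agree that a rise is measured from the start of the meal. None of them is extended to the highest excursion, and 9.9.2 cites none of them.

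**Algebra for one meal**

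Let G(t) be sensor glucose over 0–4 hours and G0 the starting average.

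- Peak level: L = max G(t).
- Excursion by the letter of 9.9.2: E_lit = max G(t) = L.
- Excursion in the sense of 9.4: E = max[G(t) − G0] = L − G0.
- Discrepancy: E_lit − E = G0.

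Illustrations, with values assumed and not taken from the documents:

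- Start 120, peak 200 mg/dL: E_lit = 200; E = 200 − 120 = 80 mg/dL.
- Peak 210 mg/dL with starts of 100, 120 and 150: E_lit = 210 each time; E = 110, 90 and 60 mg/dL.

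**Treatment contrast**

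Write Δ for LY900014 minus Humalog. Since L = E + G0, Δ(E_lit) = ΔL = ΔE + ΔG0. With an unchanged rise (ΔE = 0) and assumed premeal differences ΔG0 of −5, 0 and +5 mg/dL, the literal excursion contrast is −5, 0 and +5 mg/dL, where the contrast in rise is 0 throughout.

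The identity is exact for averages over the same meals. Model-based estimates may depart from it slightly, because the baseline covariate would differ and meals without a usable starting value would drop out of E.

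Analysing change from baseline does not repair this. Baseline for CGM variables is the lead-in value of the same variable (Table ITSM.6.2), so that step subtracts a lead-in peak and not the starting glucose of the meal.

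**The case against.** The strongest reply is that 9.9.2 is simply the derivation of the level. Its heading nearly matches the level row, its formula is the right one for that row, and 9.9.1 also concerns the level. One ungrammatical word points the other way. On that view no wrong formula is prescribed. A programmer with two differently named rows and the definition in 9.4 would most likely compute maximum minus starting glucose, so two identical rows are an unlikely result.

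Much of this stands. A reader might infer that the SAP unambiguously prescribes a peak level as the excursion; the heading of 9.9.2 does not support that. The reply still leaves the listed excursion without its own derivation, although Section 6.13 says Appendix 1 gives one. Section 9.4 shows the probable intent, but it is headed and written for mean excursions, and the only sentence that names a highest excursion gives a different rule.

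A second reply also stands. A reader might infer that the trial's evidence on the postprandial rise is compromised. The documents do not support this. Objective 12, the 1-hour excursion after breakfast, has the subtraction written into its endpoint. The mean excursions and iAUCs over 0–1, 0–2, 0–3 and 0–4 hours are all taken relative to starting glucose. The highest excursion is not among the 16 listed objectives, and there is no multiplicity adjustment in which it plays a part.

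**Conclusion.** The point holds as an internal inconsistency with two possible readings, both unsatisfactory. Literally, the excursion row repeats the level row, contradicts 9.4, and has a contrast shifted by the premeal glucose difference. With *excursions* taken as a stray word, the excursion row lacks a derivation. The documents do not settle which reading was programmed.

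The consequence is small. It is confined to one exploratory CGM variable. The primary and secondary endpoints, objective 12, the mean excursions, the iAUCs, the sample size and the alpha level are unaffected. Under the literal reading the per-meal discrepancy is the whole premeal glucose, but the shift in the contrast is only the between-treatment premeal difference. The documents give no value for that difference and no indication that one exists; the mg/dL figures above are assumptions that illustrate the algebra.

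**What to change.** In SAP 9.9.2, delete *excursions* so that the sentence derives the peak level only. Add one sentence, there or as a new 9.9.3: the highest postprandial excursion is the maximum sensor glucose over 0–4 hours after the start of the meal, under the same next-meal exclusion, minus G0, the [−19, 0] minute starting average already defined in 9.3 and 9.4. State that a meal with no CGM value in that window contributes no excursion.

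The cost is one deletion, a sentence or two of text and about one line of programming; no new data are needed. It does not change a principal feature of the protocol, so under SAP Section 6.1 it can be recorded in the SAP or the CSR without a protocol amendment. If the analysis has already been run, the CSR should say which derivation was programmed and, if it was the literal one, relabel or recompute that row.

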9.10. Other

The duration of each episode of hypoglycemia will be calculated as stop time – start time.

Leo Document ID = f90bc9b5-63f5-412e-b7e9-fde76bcbf520

Approver: PPD

Approval Date & Time: 29-Oct-2019 17:26:57 GMT

Signature meaning: Approved
